#### **4.3.2. Withdrawal From the Study**

Subjects may withdraw from the study at any time at their own request or may be withdrawn at any time at the discretion of the Investigator for safety, behavioural, or compliance reasons.

The date and the primary reason for study withdrawal will be recorded on the eCRF. If a subject is withdrawn from the study because of an AE, the Sponsor and/or designee must be notified by email or phone within 48 hours, and the specific AE leading to study withdrawal should also be identified on the eCRF.

If subjects discontinue treatment for any reason, they should complete an EOT visit at their next scheduled visit, and then have an EOS visit approximately 4 weeks following their last study drug dose.

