#### 2.2.2. Primary Efficacy Endpoint

The primary efficacy endpoint is the percent change from Baseline in SALT score at Week 24.

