#### **4.3.1. Discontinuation of Study Drug**

Subjects should be encouraged to complete study treatment. If 3 or more study doses are missed or planned to be missed, or if 2 consecutive doses are missed or planned to be missed, the Investigator in conjunction with the Sponsor study team should determine whether study drug should be discontinued permanently.

If study treatment is permanently discontinued, the subject should follow up at the next scheduled visit for end of treatment (EOT) assessments. An end of study (EOS) visit should occur approximately 4 weeks after their final study drug dose.

A subject is considered to have completed the study if he/she has completed the follow-up visit at Week 28 (Day 197).

Study drug must be discontinued if any of the following events occur:

- Subject receives or plans to receive a prohibited therapy (see Section 5.3) consistently over the course of the study.
- Subject has  $\geq$  Grade 3 hypersensitivity reactions or anaphylaxis due to study drug per Common Terminology Criteria for Adverse Events (CTCAE) criteria. [REDACTED]
- Noncompliance with study procedures and expectations.

- Subject becomes pregnant.
- Subject withdraws consent.

Other reasons study drug may be discontinued include:

- AE (the specific AE should be identified on the electronic case report form [eCRF]).
- Investigator's decision.
- Sponsor's decision.

The date and the primary reason for study drug discontinuation will be recorded on the eCRF. If a subject discontinues study drug because of an AE, the Sponsor and/or designee must be notified by email or phone as soon as possible, and the specific AE leading to study drug discontinuation should also be identified on the eCRF.

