6.2 General Considerations

All data collected during the study (data originating from the electronic Case Report Forms (eCRFs) or electronic transfers will be presented in the data listings. Event-based listings will be sorted by subject identifier and event start date/time (i.e., Adverse Event (AE) start date/time). Assessment-based listings will be sorted by parameter name (alphabetically unless specifically stated otherwise), subject identifier, visit, assessment date and time (if applicable).

Unless otherwise stated, the following methods will be applied:

- Continuous variables: Descriptive statistics will include the number of non-missing values (n), arithmetic mean, standard deviation, median, minimum, and maximum values.

The minimum and maximum values will be displayed to the same decimal precision as the source data, the arithmetic mean and median values will be displayed to one more decimal than the source data, and the standard deviation (SD) values will be displayed to two more decimals than the source data for the specific variable.

The appropriate precision for derived variables will be determined based on the precision of the data on which the derivations are based, and statistics will be presented in accordance with the abovementioned rules.

- Categorical variables: Descriptive statistics will include frequencies and percentages per category. The denominator in all percentage calculations will be the number of subjects in the relevant analysis population, unless specifically stated otherwise. Percentages will be rounded to one decimal place and will not be displayed for zero frequencies.
- Repeat/unscheduled assessments: When values collected at scheduled study visits/time points is missing, repeat or unscheduled assessments closest to the scheduled visit date within the visit window defined in Table 1 and Table 2 will be used for the visit to calculate summary statistics in summary tables with visits as defined in section 6.6. All collected data will be included in the data listings. If an unscheduled visit was intended to replace the missing assessment for a scheduled visit this should be documented clearly before values are used as a scheduled visit assessment.

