6.3 Key Definitions

The following definitions will be used:

- Date of the First Study Treatment Administration: The date of the first study treatment administration is defined as the earliest date on which a study treatment was administered.
- Baseline: The Baseline value is defined as the last available valid, non-missing observation for each subject prior to first study treatment administration on Day 1. If day 1 assessment has time missing, it will be considered as the baseline.
- Change from Baseline: The change from Baseline value at each visit will be calculated for all continuous parameters using the following formula when both values are available:

$$\text{Change from Baseline Value} = \text{Result at specified visit} - \text{Baseline Value}$$

- % Change from Baseline: The % change from baseline value is defined as Change from Baseline divided by Baseline value. Study Day: The study day of an event is defined as the relative day of the event starting with the date of the first study treatment administration (reference date) as Day 1 (there will be no Day 0).

The study day of events occurring before the first study treatment administration will be calculated as:

$$\text{Study Day} = (\text{Date of Event} - \text{Date of First Study Treatment Administration})$$

For events occurring on or after Day 1, study day will be calculated as:

$$\text{Study Day} = (\text{Date of Event} - \text{Date of First Study Treatment Administration}) + 1$$

Study days will only be calculated for events with complete dates and will be undefined for events that are ‘Ongoing’ at the end of the study.

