Time to SALT score improvement of 30% (SALT₃₀), 50% (SALT₅₀), 75% (SALT₇₅), and 90% (SALT₉₀) improvement will be summarised using the Kaplan-Meier method. For the subjects who did not achieve 30%, 50%, 75% or 90% SALT Score improvement, the week of the last SALT score assessment for the subject will be treated as censoring in these analyses. If there is no post-baseline assessment, the subject will be censored at date of first dose.

Subgroup analyses: SALT score, change from baseline and % change from baseline will be summarize by these subgroups:

- 1) By Demographics (age categories (<40, >=40), sex and race)
- 2) By Site
- 3) By Baseline SALT Score Categories (<50, >=50 - < 95, >=95)
- 4) Duration of Current AA episode (<6 months, 6 months – 1 year, > 1 year - 4 years, >4 years - 7 years)

SALT Score <=20 and <=10 and 30%, 50%, 75% and 90% improvement of SALT by visit will also be summarized by baseline SALT Score Categories (<50, >=50 - < 95, >=95).

A few SALT assessments were not assessed accurately (approval status of “No”). SALT assessments were reassessed for those cases. The SALT score analysis in this SAP is based on the SALT score data with approval status of “Yes”.

For optional scalp biopsies, listing will be prepared sorted by subject identifier for the Safety population, along with age, sex, race, and baseline weight of the Subject.

For photographs for scalp, eyebrows and eyelashes and optional photographs of body hair (growth or regrowth) and fingernails, listing will be prepared sorted by subject identifier for the Safety population, along with age, sex, race, and baseline weight of the Subject.

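### A subject who stops drug before about Week 20 is scheduled out before Week 24, so the primary efficacy value is likely to be missing and, on the visible SAP rules, the Week 24 mean would describe attenders only

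*Protocol*

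**What the plan says.** **Visits after stopping drug.** Protocol 4.3.2: "If subjects discontinue treatment for any reason, they should complete an EOT visit at their next scheduled visit". Protocol 4.3.1 sets the time of the last visit after permanent discontinuation: "An end of study (EOS) visit should occur approximately 4 weeks after their final study drug dose". Section 4.3.2 gives the same timing whatever the reason for stopping: "and then have an EOS visit approximately 4 weeks following their last study drug dose". Neither section asks for attendance at Week 24. Section 4.3.3 allows early terminators to be replaced.

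**Endpoint.** Protocol 2.2.2: "The primary efficacy endpoint is the percent change from Baseline in SALT score at Week 24". Section 2.2.4 equates Week 24 with Day 169.

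**Analysis.** SAP 7.2 uses the Safety Population (at least one dose) for efficacy. The rules that decide what happens to a subject without a Week 24 SALT are these:
- Means, SAP 6.2: "Descriptive statistics will include the number of non-missing values (n), arithmetic mean, standard deviation, median, minimum, and maximum values". Change from baseline, SAP 6.3: "will be calculated for all continuous parameters using the following formula when both values are available".
- Percentages, SAP 6.2: "The denominator in all percentage calculations will be the number of subjects in the relevant analysis population, unless specifically stated otherwise". SAP 16 names no other denominator for SALT ≤20, SALT ≤10 or SALT30/50/75/90.
- Time to SALT improvement, SAP 16, for non-achievers: "the week of the last SALT score assessment for the subject will be treated as censoring in these analyses".
- Missing scheduled values, SAP 6.2: filled from a repeat or unscheduled assessment, but only inside the visit window.

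**Not visible.** The protocol's visit schedule, SAP 6.5 and 6.7 with the window tables, and the footnotes to the EOT and EOS labels in SAP 6.6.

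**The concern.** The trial has no control arm. Protocol 1.4 justifies this by historical placebo data, so the Week 24 SALT result is what a reader will set against outside figures. Follow-up for an early stopper is tied to the last dose and not to the endpoint date, so stopping drug would usually also mean losing the primary efficacy value.

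If subjects leave because hair is not regrowing, a mean over those still attending flatters the drug. At the same visit the responder rates would keep those subjects in the denominator, so two summaries printed side by side would rest on different sets of people. Replacing early terminators restores the head count but does not recover the missing values.

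**Working it through.** **1. The plan's own figure.** The documents give no efficacy sample-size derivation to reproduce. The figure that the visit timing rests on is the maximum participation of 232 days (33 weeks) in protocol 3.3. Screening of 35 days plus Day 197 (Week 28) gives 35 + 197 = 232 days, and 232/7 = 33.1 weeks. It reproduces.

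**2. When does EOS fall before Week 24?** There are 24 weekly doses, in Weeks 0 to 23. A dose in Week w is on Day 1 + 7w, and EOS is 28 days later, on Day 29 + 7w. EOS precedes Day 169 when 29 + 7w < 169, that is, when w < 20.

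| Last dose | EOT about | EOS about | Before Day 169? |
|---|---|---|---|
| Week 9 (Day 64) | Week 10 | Week 13 (Day 92) | yes |
| Week 19 (Day 134) | Week 20 | Week 23 (Day 162) | yes |
| Week 20 (Day 141) | Week 21 | Week 24 (Day 169) | no |

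Last doses in Weeks 0 to 19, 20 of the 24 dosing weeks, lead to exit before the endpoint. The cut-off is approximate: an EOS at Week 23 might fall inside the unseen Week 24 window.

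**3. Handling on the visible SAP rules.** A subject with no Week 24 SALT has no change value and is not in the mean. The same subject remains in the Safety Population, so counts in the denominator of the SALT threshold and SALT30/50/75/90 rates without being able to count in the numerator. If not yet a responder, the subject is censored at the last SALT in the Kaplan-Meier summary.

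**4. Illustration.** The documents give no dropout rate, effect or SD, so all of these are assumed: N = 30; k = 3, 6 or 9 subjects (10%, 20% or 30%) without a Week 24 value; attenders averaging -30%; stoppers averaging s. All-treated mean = [-30(30 - k) + s·k]/30. The reported mean is -30% in every cell.

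| Stoppers' mean s | k = 3 | k = 6 | k = 9 |
|---|---|---|---|
| 0% | -27.0% | -24.0% | -21.0% |
| -15% | -28.5% | -27.0% | -25.5% |
| -30% | -30.0% | -30.0% | -30.0% |
| -45% | -31.5% | -33.0% | -34.5% |

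For k = 6 and s = 0 the gap is 6 points. With n = 24 and an assumed SD of 20 to 40, the standard error is 20/√24 = 4.08 to 40/√24 = 8.16, so the gap is 6/4.08 = 1.47 to 6/8.16 = 0.73 standard errors.

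**5. The two bases at one visit.** Six responders among 24 attenders are 6/24 = 25.0%, but 6/30 = 20.0% on the SAP denominator. The mean in the same table would use the 24.

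**The case against.** The strongest objection is that the deciding text is not visible. Protocol 6.6.2 groups Week 24 with EOT as a photography visit, and SAP 6.2 says that CRF visit information is used in the tables and that windows do not exclude assessments. If the CRF has one combined Week 24/EOT visit, an early EOT value could be tabulated as Week 24. Against that, SAP 6.6 lists Week 24 and EOT as separate labels and applies the windows of 6.7. The visible text does not settle it, so the handling in step 3 is conditional. The combined visit would not be harmless either: a last dose in Week 9 would put a Week 10 value into the Week 24 mean.

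The exit rule is also not absolute. The visit timings are worded as recommendations and are approximate, and protocol 6.3.12 lets a pregnant subject remain for follow-up. A subject who withdraws consent cannot be asked back.

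Observed-case means, an all-treated responder denominator and Kaplan-Meier censoring are ordinary choices. The responder rates, on this reading, already keep all treated subjects, so the risk of flattery reaches the mean and not those rates. The SAP also reports n with every mean, tabulates non-completion with reasons and lists all data, so a careful reader could see how many are missing. All of this stands, and it limits the point. It does not give an all-treated mean.

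A reader might infer that the SAP adopts non-responder imputation. It does not say so: that treatment is only implied by a default denominator rule that allows exceptions.

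**Conclusion.** The point holds as a conditional one and is an optional improvement. The timing is firm: a last dose before about Week 20 puts EOS before Week 24, and no visible text brings the subject back, so the primary efficacy value is likely to be missing. The split between mean and responder rates follows from the visible SAP rules. It would fall away if an unseen section keeps stoppers in SALT follow-up or sets another rule for their Week 24 value.

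Two stronger readings are tempting and unsupported. One is that the reported mean will be too favourable: under the assumed inputs the gap runs from 9 points in the drug's favour, through zero, to 4.5 points against it, depending on how stoppers fare. The other is that 20 of 24 weeks measures risk: it counts possible stop times and is not a probability. With no dropout rate in the documents, the actual size cannot be derived.

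The primary objective is safety, and the protocol says that the study is not formally powered for efficacy. What is affected is how the Week 24 result is read against historical data, not a test.

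**What to change.** **Protocol 4.3.1 and 4.3.2.** Add: a subject who stops study drug early and has not withdrawn consent is asked to attend one SALT assessment at Week 24 (Day 169), off drug, in addition to the EOT and EOS visits.

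**SAP.**
- State that an early EOT value is not tabulated as Week 24.
- Report the observed Week 24 mean with n and the number missing. Flag off-drug values with weeks since last dose and any new alopecia therapy.
- Add a sensitivity mean over all treated subjects, with missing Week 24 values set to no change and, separately, to the last available SALT. The mean and the SALT responder rates then share a denominator.

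**Cost.** One non-dosing visit per early stopper, or 3 to 9 visits at the assumed 10% to 30% stopping, all inside the existing 232-day maximum. It needs a protocol and consent amendment with ethics review, possible re-consent of current subjects, and one extra table. Recovery will be partial. Off-drug values do not measure the effect of continued dosing and may reflect other therapy, which is why they are flagged. If enrolment and treatment are finished, the SAP changes alone can still be made before database lock, with no new visits.

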#### **4.3.3. Subject Replacement**

Subjects that terminate study treatment early may be replaced as appropriate to meet the objectives of the study.

## 5. STUDY TREATMENT

Study drug is defined as EQ101 and will be supplied by the Sponsor

## 5.1. Study Drug

### 5.1.6. Modification of Dose and/or Treatment Schedule

There are no dose modifications to study drug during this study. Subjects should be encouraged to complete all dosing and visits.

### **5.1.7. Study Drug Compliance**

If subjects have missed or plan to miss  $\geq 3$  doses of study drug or 2 consecutive doses, the Investigator in conjunction with the Sponsor study team should discuss whether a subject should permanently discontinue study drug.

### **5.1.8. Study Drug Accountability**

The site will maintain the following records: receipt of shipments, dispensation to subjects, and destruction or return of partially used, or unused study drug. Upon completion or early termination (ET) of the study, all unused and partially used (if allowed by site/institutional procedure to be retained) study drug must be returned to the Sponsor or designee, unless the Sponsor authorises the study site to destroy study drug.

## **5.2. Additional Protocol Required Medication**

There are no additional protocol required medications.

## 6. STUDY PROCEDURES AND ASSESSMENTS

The following sections describe the study procedures and assessments that will be performed during the study.

### 6.1. Medical History and Demographics

#### 6.1.1. Medical History

A complete medical history and information on the subject's concurrent medical conditions will be obtained.

All findings will be recorded on the Medical History eCRF.

Details of the diagnosis and previous treatment for AA will be collected. This may include details of locations and timing of hair loss and regrowth.

#### 6.1.2. Demographics

Demographic information collected will include age, sex, race, and ethnicity. Where local regulations do not permit certain demographic data to be collected, collection of those data will not be required.

### 6.2. Prior and Concomitant Therapy

All medications taken by subjects between signing the informed consent form (ICF) and the end of the study will be recorded in the subject's eCRF. The name, dose, route, and start and stop dates of concomitant medications must be recorded. Medications include prescription and over-the-counter medications (including herbal products and vitamins). For subjects entering on a stable dose of permitted medication, any change in dose should also be recorded.

Previous treatments for AA will be recorded.

### 6.3. Safety Assessments

This section provides information on AE collection. Safety monitoring and reporting procedures are addressed in Section 8.

While pregnancy is not considered an AE, all cases of fetal drug exposure via a maternal parent as study subject or pregnancy of a partner of a male study subject will be reported immediately to the Sponsor (refer to Section 8.2.3 for reporting requirements).

#### 6.3.1. Adverse Events

An AE is any untoward medical occurrence in a clinical study participant administered a pharmaceutical product and which does not necessarily have a causal relationship with this treatment.

An AE can therefore be any unfavourable and unintended sign (including an abnormal laboratory finding), symptom, or disease temporally associated with the use of a medicinal (investigational) product, whether or not related to the medicinal (investigational) product (definition per International Council for Harmonisation [ICH]). Pre-existing events, which increase in frequency or severity or change in nature during or because of use of a drug in human clinical studies, will also be considered as AEs. AEs may also include pre- or post-treatment complications that occur as a result of protocol-mandated procedures (e.g., invasive procedures such as biopsies).

AEs will be monitored throughout the entire study. Investigators will ask the subjects at each visit if they have experienced any untoward occurrence since the last study visit. All AEs will be recorded on the CRFs provided, including: a description of the event, severity, time of occurrence, duration, any action (e.g., treatment and follow-up tests), outcome, and the Investigator's assessment of the relationship to the study treatment.

From the time of signing the ICF through the first study drug administration, all SAEs and nonserious AEs related to protocol-mandated procedures (including medication washout performed specifically for the study) will be recorded on the SAE/AE eCRF. All other untoward medical occurrences observed during Screening, including exacerbation or changes in the medical and surgical history, will be captured on the medical and surgical history eCRF. An AE does not include:

- medical or surgical procedures (i.e., surgery, endoscopy, tooth extraction, transfusion); the condition that leads to the procedure is an AE;
- pre-existing diseases or conditions present or detected prior to start of study drug administration which do not worsen;
- situations where an untoward medical occurrence has not occurred (i.e., hospitalisation for elective surgery [prolongation of hospitalisation is an AE], social and /or convenience admissions); or
- overdose of either study drug or concomitant medication without any signs or symptoms, unless the subject is hospitalised for observation.

A clinical abnormality that meets any of the following criteria should be reported as an AE:

- has accompanying symptoms and signs;
- requires additional diagnostic tests or therapeutic measures (e.g., surgical intervention);
- leads to a change in study drug dosing regimen (e.g., dose delay, discontinuation) or study termination; or
- is considered clinically significant by the Principal Investigator (PI).

Any AE where a causal relationship with the study drug is a reasonable possibility (possibly/probably or definitely related) is referred to as an **adverse drug reaction**.

An **SAE** is any AE that, at any dose:

- results in death;
- is life-threatening (the term 'life-threatening' in the definition of 'serious' refers to an event/reaction in which the participant was at risk of death at the time of the event/reaction; it does not refer to an event/reaction which hypothetically might have caused death, if it were more severe);
- requires inpatient hospitalisation or prolongation of an existing hospitalisation (only hospitalisations that are longer than expected based on PI judgement, will be considered prolonged hospitalisations);
- results in persistent or significant disability/incapacity (an AE that results in a substantial disruption of a person's ability to conduct normal life functions); or

- is a congenital anomaly/birth defect (a congenital anomaly/birth defect that occurs in the offspring of a participant exposed to the study drug).

Medical and scientific judgement should be exercised in deciding whether other situations should be considered serious, such as important medical events that may not be immediately life-threatening or result in death or hospitalisation but might jeopardise the participant or might require medical or surgical intervention to prevent one of the other outcomes listed in the above definition. These should also be considered serious.

Examples of such events are intensive treatment in an emergency room or at home for allergic bronchospasm, blood dyscrasias or convulsions that do not result in hospitalisation, or development of drug dependency or drug abuse.

A sudden unexpected serious adverse reaction (SUSAR) is an AE that meets all the following criteria:

- is serious;
- there is at least a reasonable possibility of a causal relationship between the event and the study drug;
- is considered unexpected (i.e., the event is not listed in the Investigator's Brochure [IB] or is not listed at the specificity or severity that has been observed). For example, under this definition, hepatic necrosis would be unexpected (by virtue of greater severity) if the IB referred only to elevated hepatic enzymes or hepatitis. Similarly, cerebral thromboembolism and cerebral vasculitis would be unexpected (by virtue of greater specificity) if the IB listed only cerebral vascular accidents. "Unexpected" as used in this definition, also refers to AEs that are mentioned in the IB as occurring with a class of drugs or are anticipated from the pharmacological properties of the drug but are not specifically mentioned as occurring with the particular drug under investigation.

